5.2 Training for Study Interventions

Prior to the initiation of the study, the pharmacists randomized to the intervention will participate in a two-day training conference held at the coordinating site. During this training, the dashboards functionality will be reviewed, along with the SOP manual which fully guides interventions. During this training conference, the intervention pharmacists will also participate in case-based competencies.

Sessions that occur during this conference include:

1. General overview of organ transplantation
2. Review of immunosuppression pharmacology and pharmacokinetics
3. Review of transplant immunosuppression dashboard specifics
4. Running reports to create alerts
5. Assessing clinical relevance of alerts
6. Alert categories
7. Interventions to address alerts
8. Suppressing alerts
9. Clinical and research documentation
10. Motivational interviewing techniques – face-to-face and over the phone
11. Provider collaboration strategies
12. Case-reviews

The investigational team and outside consultant experts will lead these sessions. We will also utilize expertise from the local VA and transplant center to conduct training sessions when needed. In addition, during the 24-month intervention period, we will have monthly teleconferences with the intervention pharmacists at the five sites to discuss and address issues with the dashboard and/or intervention. As an additional safety measure and to further ensure intervention fidelity, we will have experts available to discuss patient issues with sites participating in the intervention. These include the PI, transplant nephrology, transplant hepatology and an internal medicine physician. All interventions will be documented in the medical record using an approved note template. As another quality assurance step, through querying the notes entered into CPRS by intervention site pharmacists, we will capture specific interventions made by the study site pharmacists; these will be monitored by the PI and investigational team to ensure clinical appropriateness. If there are concerns with specific interventions made by study site pharmacists, these will be addressed on a case-by-case basis. During the course of the study, if an intervention pharmacist has a particular issue that is time sensitive and is unsure how to address it, they will have the ability to call and/or page the PI or investigational team, which includes expertise in transplant-related care. For non-urgent issues, pharmacists can send secure emails to investigational team members or bring up the issue during conference calls. Thus, there will be ample training and resources available to all intervention site pharmacists to ensure the study is conducted in a safe clinically appropriate manner with strong fidelity.

5.3 Usual Care

Both the control and intervention groups will continue to receive usual care as part of this study. Patients at the control sites will receive standard of care, and patients at the intervention sites will receive standard of care plus the pharmacist-led intervention. Usual care for Veteran organ transplant recipients across the 10 study sites varies somewhat, but generally includes the following: at most sites, nurse coordinators and/or mid-level practitioners are responsible for general transplant patient oversight, including ensuring laboratory assessments are scheduled/reviewed and medication regimens are accurate and up to date. However, large patient numbers and workload constraints preclude these health care professionals from prospective detailed daily monitoring of patients. If there is non-adherence to laboratory assessments or medications, they are rarely identified concurrently or early after they occur. Thus, medication safety issues that arise usually do not get identified or addressed until they have caused a clinically significant issue, leading to a health care encounter (clinic visit, ER visit, hospitalization). In addition, during this long-term ambulatory phase of care for transplant patients, pharmacists usually act as consultants and are only involved in direct patient care if an issue arises, and the nurse or provider engages the pharmacist for assistance. Within usual follow up care, pharmacists do not conduct routine daily surveillance of all transplant patients. Most transplant patients have multiple physician providers, both within and outside the VA system, providing care and medication management. This includes a primary care physician to manage common comorbidities (hypertension, diabetes, etc.) and a specialist (nephrology, hepatology) to manage allograft function; other specialists, including endocrinologists and cardiologists, are commonly involved with this patient population as well. Thus, care coordination and communication across these providers and health care organizations can often be fragmented. This usual care environment is complex and difficult to navigate, even for patients with high health literacy.^{3,18}

5.4 Adherence Assessment

To ensure fidelity across sites and efficiency for intervention providers, the specific day-to-day tasks involved with this intervention, which include running the dashboard, assessing and intervening on the alerts and appropriate follow up with patient and providers, are fully developed in the SOP manual. This manual was vetted by transplant clinicians, provided to each intervention site pharmacist with appropriate training. In addition, we will have experts available to discuss patient issues with sites participating in the intervention. These include the PI, transplant nephrology, transplant hepatology and an internist.

To assess adherence to be SOP, all interventions will be documented in the medical record using approved note templates, including a specific transplant medication monitoring note which has already been developed and is in use by pharmacists in VISN 7 and VISN 12. Through querying the notes entered into CPRS by intervention

site pharmacists, we will capture specific interventions made by the study site pharmacists; these will be monitored by the PI and investigational team to ensure clinical appropriateness. This is particularly the case for interventions involving changes in immunosuppression regimens. If there are concerns with specific interventions made by study site pharmacists, these will be addressed on a case-by-case basis. During the course of the study, if an intervention pharmacist has a particular issue that is time sensitive and is unsure how to address it, they will have the ability to call and/or page the PI or investigational team, which includes expertise in transplant-related care. For non-urgent issues, pharmacists can send secure emails to investigational team members or bring up the issue during conference calls.

Adherence to the intervention and the SOP manual will be monitored by the coordinating study site. Specific interventions will be reviewed in a concurrent fashion. All deviations or issues that are identified will be reviewed by the study team and addressed. If a concerning pattern of non-adherence develops at a particular study site, the PI, in conjunction with the Co-Is and data safety monitoring team as the right to remove that site from the study. Replacement of a site will depend on criteria discussed in the study enrollment procedures section of this protocol.

6 STUDY PROCEDURES

Because of the nature of this intervention, all care that is provided, including laboratory and clinic visits, will be considered as usual care. The intervention consists of increased review of patients by a pharmacists and increased scrutiny of patients' medication regimens and laboratory values, through the use of a dashboard surveillance system. However, any interventions that are made as a result of this increased review will be considered usual care as they are directly related to monitoring of the organ transplant and immunosuppression medications. Thus, there are no study procedures that will occur above and beyond usual care procedures, which are described in the usual care section of this protocol.

The procedures unique to this study includes randomization of sites to use of the dashboard (intervention) or usual patient care review, training of the five intervention site pharmacists, site initiation and monitoring of intervention integrity and fidelity during the 24-month intervention phase of the study. No patient-specific procedures or interventions will occur that are above and beyond usual care will occur as part of this study.

7 SAFETY ASSESSMENTS

The impact of study interventions on patient outcomes will be closely monitored by an internal oversight committee (IOC). The IOC will consist of the PI, co-investigators, study coordinator, data manager and consultants on the proposal. The functions of the IOC will include: 1) providing scientific oversight; 2) reviewing all serious adverse events (graft loss and death events, compared across intervention groups) or complications related to the study; 3) monitoring site adherence to the intervention; 4) reviewing

summary reports relating to compliance with research protocol requirements; and 5) providing advice on resource allocation. The IOC will meet bi-annually and as necessary by telephone. The recommendations of the IOC will be reviewed and the PI will take appropriate corrective actions as needed. As part of this oversight, we will also recruit an independent transplant nephrologist that is not affiliated with this study to provide their expertise and review of all study activities. This expert will conduct the following:

- 1) Review the research protocol and plans for data and safety monitoring.
- 2) Evaluate the progress of the intervention, including periodic assessments of data quality and timeliness, site enrollment and retention, participant risk versus benefit, integrity of the intervention, and other factors that can affect study outcome.
- 3) Consider factors external to the study when interpreting the data, such as scientific or clinical developments that may impact the safety of study participants or the ethics of the study.
- 4) Make recommendations to the IOC, IRB, and VA R&D/VA HSR&D for continuation or termination of the study.
- 5) Protect the confidentiality of study data and monitoring.

The independent transplant nephrologist will have the authority to discontinue the trial temporarily or permanently if they perceive that harm is occurring due to the intervention. They will meet with the IOC to review serious adverse event reports, patient complaints if any, and site issues. Data will be provided at these meetings on key variables that may indicate harm, including, hospitalizations, ED visits, graft loss and death. The IOC biostatistician will evaluate the confidentiality and integrity of the database and the procedures for recording and storing confidential files. The independent transplant nephrologist will also review the elements of the plan to manage emergencies.

7.1 Serious Adverse Events (SAEs)

The intervention for this trial does not involve the administration of medications or investigational agents, but rather supplemental pharmacist-led care provided in addition to usual care already delivered to veteran organ transplant recipients. Thus, the intervention is considered minimal risk research. As part of this study, SAEs will be monitored, compared between the intervention and usual care group and reported to the IOC and independent transplant nephrologist on a bi-annual basis.

SAEs are defined as hospitalizations, ED visits, graft loss and death. Hospitalizations and ED visits will be obtained from VA CDW data housed in the VINCI environment. Graft loss events will be obtained from SRTR data linked to the VA data, while death will be obtained from both SRTR and VA CDW data. Due to the minimal risk of this study intervention and the fact that the intervention does not involve the administration of investigational agents, adverse events, including abnormalities in laboratory values, new syndromes or diseases or new or worsening patient symptoms will not be monitored or reported as a part of this study. These will be monitored and addressed under normal usual care provided to the veteran at the study sites.

7.2 Reporting Procedures

All reporting of safety concerns will occur through the IOC, as described above. The IOC will meet bi-annually and as necessary by telephone. The IOC will review reports created by the study biostatistician which incorporate clinical outcomes and SAEs, including rates of hospitalization, ED visits, graft loss and death, compared between the two groups. The recommendations of the IOC will be reviewed and the PI will take appropriate corrective actions as needed. As part of this oversight, we will also recruit an independent transplant nephrologist that is not affiliated with this study to provide their expertise and review of all study activities. This expert will conduct the following:

- 1) Review the research protocol and plans for data and safety monitoring.
- 2) Evaluate the progress of the intervention, including periodic assessments of data quality and timeliness, site enrollment and retention, participant risk versus benefit, integrity of the intervention, and other factors that can affect study outcome.
- 3) Consider factors external to the study when interpreting the data, such as scientific or clinical developments that may impact the safety of study participants or the ethics of the study.
- 4) Make recommendations to the internal IOC, IRB, and VA R&D/VA HSR&D for continuation or termination of the study.
- 5) Protect the confidentiality of study data and monitoring.

8 INTERVENTION DISCONTINUATION

The intervention will be discontinued based on the recommendations of the IOC and/or the expert transplant nephrologist opinion. These decisions will be based on bi-annual reports provided by the study biostatistician that will report SAE rates compared between the intervention and usual care groups. Discontinuation will be recommended if the intervention demonstrates increased harm or potential harm to veterans at sites randomized to the intervention. This decision will be made based on clinically or statistically significant differences that are apparent in SAE rates between intervention and usual care sites. Worrisome trends will also be considered in the IOC decision.

The study sample size and power analyses were not designed to specifically conduct interim analyses for outcomes and factor in early termination due to substantial improvements or futility. Thus, only safety concerns will be used as criteria for early stoppage.

If a particular site discontinues the intervention or usual care, attempts will be made to replace the site if possible. However, if the site discontinues the study after considerable intervention time has elapsed, data collection for follow up outcomes will be locked at that time point and a replacement site will not be recruited.

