4 SELECTION AND ENROLLMENT OF STUDY SITES AND PATIENTS

Patients will be included in this study if they are veteran organ transplant recipients that receive immunosuppressant medications through the VA system. Organ transplant recipients will be identified using ICD-9/10 codes from the VA electronic health record (CPRS), with this data housed in the CDW. Once identified, active medications will be queried and those receiving immunosuppressant medications to prevent rejection (tacrolimus, cyclosporine, azathioprine, mycophenolate, sirolimus, everolimus, or belatacept) will be included in the study. There are no exclusion criteria for patients in this study as recruitment is at the VA site-level. As this is a cluster-randomized study and randomization will occur at the site level and not the patient-level, participants will not be recruited for the study, and data collection will occur through querying and linking the VA CDW, the SRTR transplant registry and CMS data repositories. We will request waiver of written documentation of patient informed consent. We will also request HIPAA authorization waiver as well for all patients. The following protected health information (PHI) elements will be required to complete the study with the HIPAA authorization waiver.

| PHI Required for Study | Rationale |
|--|---|
| Social Security Number | Require real SSNs to create finder file and send to Scientific Registry of Transplant Recipients (SRTR) to acquire baseline transplant information and graft outcomes |
| Date of transplant, date of clinical events (including graft loss, rejections, | Require dates to ensure events occurred during the study period and to conduct |

| | |
|--|--|
| hospitalizations, emergency department visits and death) | time to event survival analyses for primary and secondary aims |
| Zip codes | Require zip code to assess and adjust for potential geographic confounding in multivariable analyses |

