4.2 Exclusion Criteria

- There are no exclusion criteria for patients in this study as recruitment is at the level of the VA site.
- All veterans meeting inclusion criteria will be monitored by the dashboard system and will be included in the outcomes assessment. Patients may enter or exit the study in a rolling manner, which will be accounted for during analyses.

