9.3.1 Primary outcome

The primary outcome for this study will include the overall rate of ER visits and hospitalizations, compared between the intervention and control groups. These encounters will be captured electronically throughout the 24-month study through the use of the CDW, stored in the VINCI environment. In addition, to ensure encounters are captured in a comprehensive manner, we will also link the VA CDW data to CMS (Medicare) claims data and capture non-VA ER and hospitalization encounters (after study completion). As most transplant patients are dual users and have Medicare

insurance benefits, this linkage will provide a more accurate assessment of these health care utilization.³ We expect ER visits and hospitalizations to significantly decrease within the intervention arm, towards the latter half (second 12-months) of the study due to a lag effect of the intervention on this outcome. This expectation is based on our previous research in this field and assessment of pharmacist interventions on medication safety and reduced adverse drug events requiring hospitalization. ER visits and hospitalizations will be assessed and compared as described in the statistical analysis plan. These will be defined based on encounter criteria within the CDW and CMS data: all-cause ER visits and all-cause hospitalizations leading to at least one overnight stay will be included as events.

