9.4 Data Analyses

The data analysis will incorporate the intent-to-treat principle; namely, all participants enrolled in the intervention group will be included in the analysis and compared to all of the patients captured within the control group. If a patient dies, has graft loss or moves out of their study site, their data will be censored at that time point. For comparative statistical assessments within the utilization outcomes, the two groups will be compared using a generalized linear mixed models (GLMM) approach.⁵⁴ This approach allows for measurement of participants at different time points, clustering by study site, missing data under the assumption of missing at random (MAR), time varying or invariant covariates, and can also account for the effect of correlated longitudinal measurements within participants. In addition, GLMM accommodates a wide range of distributional assumptions such as dichotomous (e.g. binomial), count (e.g. Poisson), continuous

(e.g. Gaussian), and categorical or ordinal outcomes. For comparing the primary outcome (ED visit and hospitalization rates), we will use GLMM (with appropriate link function) with counts of these events as the outcome variable and intervention group (yes/no) as the primary independent variable. This analysis is equivalent to Poisson regression or negative binomial regression (in the case of over-dispersion), both special cases of GLMM. Additional adjustment covariables will be added to the model in a second set of analyses. Covariates will include patient sociodemographics: age, sex, race, comorbidities (using modified Elixhauser definitions), marital status and education. In these models, donor information (age, sex, race, deceased or living) and transplant characteristics (HLA mismatches, ischemic times, panel reactive antibody levels, time since transplant) will also be included. This will assist in making valid intervention effect estimates after accounting for baseline differences, as there may be patient-level differences between groups. The magnitude of between intervention differences on outcome variables (effect sizes) at each time point will be estimated using appropriate contrasts in the corresponding GLMM models.

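### Section 8 locks outcome collection for a whole site that stops late, although section 9.4 commits to intent-to-treat with only patient-level censoring listed and outcomes come from central records

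*Combined protocol and SAP*

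**What the plan says.** Section 8 (Intervention Discontinuation) covers a site, in either arm, that stops. An attempt is made to replace it. If it leaves the study after an amount of intervention time called considerable but not defined, "data collection for follow up outcomes will be locked at that time point and a replacement site will not be recruited".

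Section 9.4 opens its analysis plan with "The data analysis will incorporate the intent-to-treat principle" and then lists its censoring events: "If a patient dies, has graft loss or moves out of their study site, their data will be censored at that time point". All three concern the patient. No site-level stop is mentioned there. Section 4.2 adds "Patients may enter or exit the study in a rolling manner, which will be accounted for during analyses", again about patients.

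On data sources, section 4 says that "data collection will occur through querying and linking the VA CDW, the SRTR transplant registry and CMS data repositories". Sections 9.3.1 and 10.1 agree, and non-VA encounters are linked only once the study is complete. Section 9.3.1 expects the reduction in events "towards the latter half (second 12-months) of the study due to a lag effect of the intervention on this outcome".

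Sections 5.4 and 10.3.4 allow a site to be removed or discontinued for repeated non-adherence or protocol deviations.

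**The concern.** A comparison by intent-to-treat needs outcomes for the patients of every randomized site over the planned period, whether or not the site kept delivering its assigned care. The lock gives up part of that follow-up, and no step described in the documents needs the site's participation to obtain hospitalizations, ER visits, graft loss or death.

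Three things make this matter with five sites per arm. First, a late stop removes follow-up from the period in which the effect is expected. Second, adherence to the intervention manual is monitored only where the intervention is delivered, so a stop for poor adherence can fall on one arm and be related to how well the intervention was working. Third, what happens to event rates at a site after it stops is what an intent-to-treat estimate should include, and the lock removes the data that would show it.

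**Working it through.** **1. The plan's own figure.** Inputs from section 9.2: 1.269 ED visits per person-year, 25% relative decrease, ICC 0.05, two-sided alpha 0.05, 80% power, 10 sites, N = 1,350. Two years per patient is assumed from the 24-month follow-up.

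- Per arm before clustering: (1.960 + 0.842)² × [1/(1.269×2) + 1/(1.269×0.75×2)] / (ln 0.75)² = 87.2.
- Design effect: 1 + (135 − 1)×0.05 = 7.7.
- Total: 2 × 87.2 × 7.7 = 1,343, against 1,350 stated. Dividing 1,350 by 0.85 gives 1,589, against 1,600 stated.

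The stated sample size reproduces and is not in question.

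**2. Follow-up removed.** For a site with share s of its arm, locked at month t ≥ 12: arm person-time lost = s(24 − t)/24; months 13-24 lost = s(24 − t)/12.

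| Site | Lock | Arm person-time | Arm months 13-24 |
|---|---|---|---|
| Equal sites, s = 0.20 | month 12 | 10% | 20% |
| Equal sites, s = 0.20 | month 18 | 5% | 10% |
| 100 of 844.5 patients (assumed) | month 12 | 5.9% | 11.8% |
| 250 of 844.5 patients (assumed) | month 12 | 14.8% | 29.6% |

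The arm size is 1,689/2 = 844.5.

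**3. Effect wanes at the stopped site, pooled person-time.** Assumptions: five equal intervention sites (120 site-months), one stops at month t, and its rate then returns to the control rate.

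Constant rate ratio 0.75, t = 12: full follow-up (4×24×0.75 + 12×0.75 + 12×1)/120 = 93/120 = 0.775; locked (72 + 9)/108 = 0.750.

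Late effect (1.0 in year 1, 0.5 in year 2), t = 12: full (72 + 12 + 12)/120 = 0.800; locked (72 + 12)/108 = 0.778.

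| Scenario | Stop | Full | Locked |
|---|---|---|---|
| Constant 0.75 | month 6 | 0.788 | 0.750 |
| Constant 0.75 | month 12 | 0.775 | 0.750 |
| Constant 0.75 | month 18 | 0.763 | 0.750 |
| 1.0 then 0.5 | month 6 | 0.800 | 0.765 |
| 1.0 then 0.5 | month 12 | 0.800 | 0.778 |
| 1.0 then 0.5 | month 18 | 0.775 | 0.763 |

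In every row the locked value is more favourable to the intervention, by 0.01 to 0.04.

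**4. The same question with site weights, lock at month 12.** This is closer to a random-intercept model with one common rate ratio. Patients per site: 1,689×0.85/10 = 143.6. Between-site variance of the log rate, from the ICC: 0.05/(0.95×2.538) = 0.0207, and ln(1.0207) = 0.0205. Site weight = 1/(0.0205 + 1/expected events); estimate = exp(Σ w·ln RR / Σ w).

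| Assumed rate ratio, year 1 / year 2 | Locked | Full, effect persists | Full, effect vanishes |
|---|---|---|---|
| 1.0 / 0.5 | 0.792 | 0.750 | 0.796 |
| 0.9 / 0.6 | 0.776 | 0.750 | 0.787 |
| 0.75 / 0.75 | 0.750 | 0.750 | 0.774 |

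Random-intercept Poisson fits to simulated data (2,000 runs) agree to within about 0.002. Where the effect vanishes, the lock favours the intervention by 0.004, 0.011 and 0.024. Where it is late and persists, the locked value lies up to 0.042 toward the null.

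**5. Adding a group-by-period term.** With one intervention site locked at month 12 and the effect persisting, a random-intercept Poisson with this term (400 simulated runs) gave 0.998 and 0.497 for true 1.0 and 0.5, averaging 0.748. For true 0.9 and 0.6 it gave 0.900 and 0.601, averaging 0.751. The shift toward the null disappears. A period term cannot recover the waning case, because the stopped site has no months 13-24 data to enter.

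**6. Power, equal sites, month 12, normal approximation.** Under the plan's method, effective events are 675/7.7×2×1.269 = 222.5 (control) and 166.9 (intervention), giving 80.2%. Multiplying the intervention events by 0.90 gives 77.8%, a loss of 2.4 points. Under the weights in step 4, the arm keeps 97.4% of its information and power goes from 84.0% to 83.5%, a loss of 0.5 points.

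**The case against.** The strongest reply is that this is one combined document. Section 9.4 does not call its censoring list exhaustive, so a site-level rule in section 8 need not be repeated there. The model is said to handle data missing at random, with diagnostics and imputation described, and "outcome variables (effect sizes) at each time point will be estimated using appropriate contrasts in the corresponding GLMM models". The lock applies when a site leaves the study, which is narrower than ceasing the intervention and may mean that permission to use its data has ended. The event is hypothetical and the precision loss is small.

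Much of this stands. The period-specific contrasts do answer the late-and-persisting case, so a reader who infers a general 4-point bias toward the null goes further than the plan supports: that shift needs a single common rate ratio. The power loss is minor. The documents do not say whether approval for extraction continues after a site stops, and if it is withdrawn, censoring at that date is close to the present lock.

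What does not stand is reliance on missing at random. The assumption is stated generally and is not argued for a site stopped over poor adherence. The data would also be missing because the plan chose to stop collecting them. The rolling-exit sentence names patients and gives no method.

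**Conclusion.** The concern holds as a conflict between a stated rule and the stated analysis principle. Following section 8 would discard follow-up that the documents give no data-source reason to lose. The main harm arises if the effect wanes at a stopped intervention site: the locked estimate is then more favourable than the intent-to-treat value, by about 0.01 to 0.04 in the rate ratio with pooled person-time and 0.004 to 0.024 with site weights at month 12. These figures assume equal sites, one stop, and a return to the control rate. If the effect is constant and persists, there is no shift.

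Two stronger readings are not supported. A reader might infer that a stopped site is excluded; its data up to the lock stay in the assigned arm, so this is unplanned administrative censoring. A reader might also infer that sites removed for non-adherence lose their data; sections 5.4 and 10.3.4 do not say so. That point, and the analysis of a site added after the single randomization in section 9.2.1, are matters for clarification only.

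**What to change.** In section 8, with a cross-reference in section 9.4, replace the lock with a rule such as: *Every randomized site stays in the primary analysis in its assigned arm, and outcomes for its eligible patients are extracted centrally for the full 24 months, subject to the patient-level censoring in 9.4. If approval for extraction is withdrawn, the site is censored at that date and this is reported by arm.*

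As clarifications, state in sections 4.3, 5.4 and 10.3.4 that a removed site's data are kept, and say how a site added after randomization is analysed; restricting it to a sensitivity analysis is one option. Decisions to stop, retrain or remove a site are unaffected.

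The cost is wording, plus confirmation from the central IRB and R&D that extraction may continue after a site stops. Keeping a site that delivers little may make the estimate more conservative. The rule should be settled before any site stops, so that it cannot be chosen in the light of outcomes.
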